#### Blinded evaluator at the site

The blinded evaluator at the site will be independent of the study conduct and blinded against the randomization code of each subject until data base lock.C The following measures will be taken to ensure the blinded evaluator at the site throughout the clinical investigation:

- Each site has to install two types of study personnel:
  - Unblinded site staff (i.e., treating investigator, other site staff)
  - Blinded evaluator at the site.

Of note, unblinded site staff as well as CRO staff (including Clinical Research Associates (CRAs)), data managers, medical monitor and biostatistician) and sponsor will be unblinded to the treatment group assignment.

- The treating investigator, all other unblinded site and CRO / sponsor staff must not disclose the blinded evaluator at the site the identity of the treatment group the subjects belong to. Especially the treating investigator must ensure that the blinded evaluator at the site is not inadvertently unblinded when evaluating the subjects.
- The blinded evaluator at the site will not be present during treating investigator's evaluation of the subject or vice versa.
- The treating investigator and the blinded evaluator at the site will not discuss any details or guesses about the treatment assignment, potential touch-up or repeat-treatment, or results of assessments in individual subjects during the course of the investigation and until the final database lock. The same applies to any discussions between blinded evaluators at the site.
- The treating investigator will explain to each subject that they should not discuss, any side-effects or complaints, nor personal views on treatment success with the blinded evaluator at the site, in order to assure scientific rigor and unbiased results of the trial.
- Results of ratings will be documented on Rating Sheets by the blinded evaluator at the site (see section 6.4.12 for details).
- The blinded evaluator at the site will not have access to the subject's source records during the course of the investigation and until the final database lock. If this will not be technically feasible, e.g., in case of electronic source records, the blinded evaluator will commit to abstain from accessing these records and will maintain the list of prohibited medical files to avoid accidental access

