# 6.3.6 Withdrawal criteria and procedures

The subject **MUST** be withdrawn from the investigation for any of the following reasons:

1. Withdrawal of consent: At any time during the investigation and without giving reasons, a subject may decline to participate further. The subject will not suffer any disadvantage as a result.

The subject **MAY** be withdrawn from the investigation for any of the following reasons:

- 1. Occurrence of an AE which requires a premature termination of the treatment or precludes followup of the subject (e.g., COVID-19)
- 2. A major CIP deviation, which may interfere with evaluation of the treatment outcome (e.g., additional aesthetic correction of the defect during the course of the investigation, use of prohibited medication, or similar)
- 3. Investigator's decision, triggered by safety, behavioural or administrative reasons
- 4. Pregnancy; **Note:** pregnant women **must** be withdrawn from **further treatment**; However, pregnant women may remain in the study for safety assessments during the scheduled study visits.
- 5. Subjects with abnormal clinically significant changes in visual examination after treatment **must** be withdrawn from **further treatment** in case an eye specialist confirms that the result is related to a vascular injection of the dermal filler (see section 6.4.8 and section 16.1).

The subjects may remain in the study at least for safety assessments during the scheduled study visits.

6. Subjects who experience neurological symptoms indicative of a vaso-occlusional event after treatment **must** be withdrawn from **further treatment** in case a neurologist confirms that the result is related to a vascular injection of the dermal filler (see section 6.4.9, also see section 16.1).

The subjects may remain in the study at least for safety assessments during the scheduled study visits.

Reasons, circumstances and findings related to early withdrawal should be fully described in the subject's source records and the eCRF respecting the subject's rights.

Attempts should be made to perform an early termination visit, which should consist of the assessments planned for Visit 9 (SV1), Visit SV2 to SV4 or Visit RT5 (depending on the study phase) – also see section 6.5.16. In the event that the withdrawal is caused by an AE, the procedures stated in section 14 must be followed.

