## 6.3.7 Replacement of subjects

Subjects withdrawn from the investigation or lost for follow-up will not be replaced.

No re-screening is allowed. An exception may be granted with prior approval of the sponsor in case that subjects are withdrawn due to restrictions that might occur in the context of the ongoing COVID-19 pandemic (e.g., in case conduction of the clinical investigation in a protocol-conformal manner is no longer possible due to a new pandemic situation comparable to the COVID-19 pandemic in spring 2020).

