## 6.3.9 Prohibited treatments

The following medications and treatments are **prohibited prior to start** of the investigation (Visit 1) and **during the entire investigation**, if not stated otherwise below (also refer to the respective ExC in section 6.3.3 to 6.3.5):

- History or presence of any autoimmune or connective tissue disease, or current treatment with immune therapy
- Previous facial plastic surgery, tissue augmentation with silicone, fat or another non-absorbable substance (permanent fillers) in the area of device application and during the entire investigation
- Implantation of dermal fillers in the treatment area within the preceding 24 months prior to Visit 1 (Screening) and during the entire investigation
- Subject has received any of the following aesthetic treatments in the midface area, e.g.
  - laser therapy, absorbable and non-absorbable sutures (threads), dermabrasion, mesotherapy, micro-needling and/or botulinum toxin (including treatment of crow's feet in the outer eye region) within the last 12 months prior to Visit 1 and during the entire investigation
  - o chemical peeling within the last three months prior to Visit 1 and during the entire

investigation,

or is planning to undergo such procedures during the investigation

- Facial lipolysis, including submental fat treatments, within the previous 12 months prior to Visit 1 (Screening) and during the entire investigation
- Bariatric surgery within 12 months prior to Visit 1 (Screening) and during the entire investigation
- Anticoagulant, antiplatelet, or thrombolytic drugs, or anti-inflammatory drugs (oral/injectable corticosteroids or non-steroidal anti-inflammatory drugs, e.g., Motrin® or Advil®) or other substances known to increase coagulation time (vitamins or herbal supplements, e.g., St. John's Wort, high doses of vitamin E supplements) from ten days pre- until seven days after each injection of the device
- Planned dental/oral surgery or modification (bridge-work, implants) within four weeks prior to baseline and repeat-treatment device injection and to a minimum of four weeks post device injections
- Current or previous treatment with another investigational drug and/or medical device or participation in another clinical study (within 30 days of Visit 1 (Screening) and entire investigation)
- Change in eating habits that result in a weight gain or loss >10% during the entire investigation

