#### Full Analysis Set (FAS)

The FAS consists of all randomized subjects who received at least one administration of the test device or the comparator device. The statistical evaluation of the FAS will follow the intention-to-treat (ITT) principle and subjects will contribute to the evaluation "as randomized".

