## 7.3.7 Effectiveness endpoints

#### Primary effectiveness endpoint

The PPS and the FAS will be both considered equally important for the primary analysis. The analysis of the primary endpoint will be performed on the PPS (primarily) and FAS. Confirmatory testing will be performed in a hierarchical ordering. Non-inferiority is demonstrated only if the results are consistent for both analysis populations.

Subjects with missing baseline MVDS score and / or missing MVDS score at Week 24 after last injection of the initial treatment phase will be considered as non-responders for the primary analysis on the FAS.

To calculate the primary outcome measure, the improvement over Baseline in the MVDS score assessed live by the blinded evaluator at the site at Week 24 after last injection of the initial treatment phase by subtracting the Midface Scale grade obtained at Baseline. The proportion of subjects with MVDS score improvement of  $\geq 1$  point will be then calculated for each treatment group.

The primary outcome measure for effectiveness will be evaluated by means of a one-sided two-group Farrington-Manning test of proportions with the following hypotheses:

- H0:  $pA pB \le d0$
- $\circ \qquad H1: pA pB > d0.$

At this, pA is the response rate for saypha® VOLUME Lidocaine and pB is the response rate for , and d0 equals to -0.1. Thus, a negative value for this difference means that the response rate of saypha® VOLUME Lidocaine is lower than the response rate for In addition to this, the response rates for both treatment groups along with their Clopper-

Pearson exact 95% CIs will be tabulated.

The study decision will be based on a Farrington-Manning-statistics with a one-sided type I error rate level of 0.025.

In addition, **sensitivity analyses** of the primary effectiveness endpoint will be performed on the FAS addressing the different reasons for non-adherence and covering the following aspects (among others) to underline the robustness of the results:

- Complete case analysis: In this analysis only those subjects will be included for whom the primary endpoint could be calculated;
- Subjects with non-allowed concomitant medication / treatments before Week 24 after last injection of the initial treatment phase may be regarded as non-responder.
- Multiple imputation under MNAR assumption for imputing missing MVDS scores at Week 24 assessed live by the blinded evaluator.

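### Outside midface correction before Week 24 has no fixed score in the primary FAS analysis: the observed rating counts if the subject is retained, non-response if the device-aware investigator withdraws them

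*Protocol*

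**What the plan says.** All references are to the protocol; the SAP was not available.

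- **Primary rule (7.3.7).** Subjects with a missing baseline or Week 24 score "will be considered as non-responders for the primary analysis on the FAS". No other non-response rule is given for that analysis.
- **FAS (7.2).** "The statistical evaluation of the FAS will follow the intention-to-treat (ITT) principle", with subjects analysed as randomized. An observed Week 24 score stands.
- **Prohibited treatment.** Section 6.3.9 bars "Implantation of dermal fillers in the treatment area within the preceding 24 months prior to Visit 1 (Screening) and during the entire investigation", along with facial surgery, fat or other permanent augmentation, threads and, around each injection, anti-inflammatory and anticoagulant drugs.
- **Scoring after prohibited treatment (7.3.7).** One sensitivity analysis on the FAS: "Subjects with non-allowed concomitant medication / treatments before Week 24 after last injection of the initial treatment phase may be regarded as non-responder".
- **Withdrawal (6.3.6).** The list of reasons for which a subject may be withdrawn includes a major deviation, with the examples "additional aesthetic correction of the defect during the course of the investigation, use of prohibited medication, or similar", and also "Investigator's decision, triggered by safety, behavioural or administrative reasons".
- **Blinding (6.1.3).** The treating investigator is unblinded. The evaluator who gives the rating is blinded and has no access to source records or the eCRF.
- **Decision (7.3.7, 7.2).** FAS and PPS must agree. Exclusion from the PPS is rated deviation by deviation at the Data Review Meeting, against criteria set in a Protocol Deviation Manual.

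**The concern.** Take a subject with a poor result who obtains another filler in the cheek at, say, Week 12. If the subject stays in, the evaluator grades a face that carries the other product, and a one-grade improvement is enough to count as a response. If the treating investigator uses the optional withdrawal, the Week 24 score is missing and the subject is a non-responder. An early termination visit asks for an MVDSS rating (6.5.16), but nothing lets that rating stand in for Week 24. One event thus has two opposite primary outcomes, and the choice lies with someone who knows the device.

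At stake is the direction of error in a non-inferiority trial. Turning failures into responses narrows the difference when the test arm has more failures to correct. Unequal retention moves the FAS difference directly.

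**Working it through.** **Inputs.** Margin −10 points; Farrington-Manning test, one-sided 0.025; test rate 85.6%; 2:1 allocation; 437 evaluable, 291 of them test, so 146 comparator; 486 randomized as 324:162 (7.1, 7.3.7, 6.3.1). The comparator rate is blacked out and is assumed to be 85.6%. The share of subjects with outside correction is also assumed, because the protocol gives none.

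**The plan's own figures.** Comparator n = (1.960 + 0.842)² × 0.856 × 0.144 × (1 + ½) / 0.10² = 145.1, so 146. Twice that is 292, total 438 against the stated 437. 437 / 0.90 = 485.6, so 486. Farrington-Manning power at 291:146 with equal rates is 83.6%, against the 83% in the log for Amendment 5. Comparator rates of 84%, 85%, 86% and 87% would give 91.1%, 86.8%, 81.1% and 73.9%, so equal rates fit best.

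**Test statistic.** z = (p̂A − p̂B + 0.10) / √[p̃A(1 − p̃A)/nA + p̃B(1 − p̃B)/nB], where p̃ are the maximum-likelihood rates constrained to p̃A − p̃B = −0.10. Non-inferiority is shown if z ≥ 1.96.

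**Model at the margin.** pA = 75.6%, pB = 85.6%, 324:162. True non-responders: 324 × 0.244 = 79.1 test and 162 × 0.144 = 23.3 comparator. A fraction f of them is corrected elsewhere. In the FAS they become responders. In the PPS they are removed, with no other exclusions.

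**Expected shift.**
- f = 10% in both arms. FAS: −10 + 10 × (0.244 − 0.144) = −9.0 points. PPS: 0.756/0.9756 − 0.856/0.9856 = −9.4 points.
- f = 10% in the test arm only. FAS: −10 + 2.44 = −7.6 points. PPS: 0.756/0.9756 − 0.856 = −8.1 points.
- An equal 2% of each whole arm, all non-responders. FAS: −10 points, no shift. PPS: 0.756/0.98 − 0.856/0.98 = −10.2 points, slightly harder to pass.

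**One-sided error** (400,000 simulated trials per row; repeat runs agree within about 0.1 point; exact FAS value with no correction 2.6%):

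| Outside correction before Week 24 | Subjects, test + comparator | FAS | PPS | Both |
|---|---|---|---|---|
| None | 0 | 2.6–2.7% | 2.6–2.7% | 2.6–2.7% |
| 5% of non-responders, each arm | 4.0 + 1.2 | 3.7% | 3.3% | 3.2% |
| 10% of non-responders, each arm | 7.9 + 2.3 | 5.0% | 4.0% | 3.9% |
| 10% of non-responders, test only | 7.9 + 0 | 10.8% | 8.0% | 8.0% |
| 1% of each whole arm | 3.2 + 1.6 | 2.6% | 2.4% | 2.4% |
| 2% of each whole arm | 6.5 + 3.2 | 2.7% | 2.3% | 2.3% |

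With correction in the test arm only at 1% or 2% of non-responders (about one or two subjects), the two-population error is 3.0% or 3.3%.

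**Unequal retention.** Suppose equal shares of each arm are corrected, with test subjects retained and comparator subjects withdrawn. The FAS error is 4.7% at 1% of each arm and 8.4% at 2%. If the PPS excludes all of these subjects in both arms, its error is 2.3% and 2.2%, which caps the joint decision. If it excludes them in the test arm only, its error at 2% is 6.2% to 6.5%. If it excludes none of the retained subjects, it scores them as the FAS does.

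**Under one fixed non-responder rule** the FAS error returns to about 2.6%. Because both populations must succeed, that also caps the joint error.

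**The case against.** The strongest reply is that scoring observed data whatever else was received is ordinary intention-to-treat handling, and that counting outside correction as failure is a different estimand. That would stand if the plan did it throughout. It does not: the withdrawn subject with the same event is not scored as observed.

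It is also fair that the event is prohibited, is named as a major deviation, can lead to PPS exclusion under criteria fixed before analysis, and has a sensitivity analysis. These reduce the problem without settling it. The PPS rating is case by case, and the sensitivity analysis is optional and decides nothing. Nor can the SAP change the primary rule alone: section 7.7 asks for a protocol amendment when a deviation affects the effectiveness analysis.

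Three stronger readings are tempting and not supported:

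- That outside correction always favours non-inferiority in both populations. It needs correction to track failure, or unequal handling by arm; equal shares of both arms give no inflation.
- That the trial's error is 5.0% or 10.8%. Those are FAS figures, and both populations must succeed.
- That a subject who takes an anti-inflammatory drug soon after injection becomes a non-responder. The wording only permits this, and only in a sensitivity analysis.

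Nothing in the protocol suggests that investigators would in fact retain or withdraw differently by arm.

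**Conclusion.** The point holds as an inconsistency in the primary scoring rule: the same event gives opposite outcomes depending on an optional decision by an unblinded person. Its size is modest under even-handed assumptions, with a two-population error of about 3.2% to 3.9% against 2.6–2.7%. It reaches 8.0% only if about eight test subjects and no comparator subjects are corrected. In a borderline result a single subject can decide: with 139 of 162 comparator responders, the FAS test fails at 266 of 324 test responders (z = 1.896) and passes at 267 (z = 1.998).

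This rests on the assumed comparator rate, on assumed frequencies of correction, on PPS exclusion of corrected subjects, and on the inference that a corrected face will usually be rated as improved. It is worth fixing because the fix is cheap, not because a large bias has been shown.

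**What to change.** In 7.3.7 and the synopsis, state that in the primary FAS analysis a subject is a non-responder if, before the Week 24 rating, they had a prohibited treatment in the treatment area that can itself add or restore midface volume, whether or not they were withdrawn. Examples are non-study filler, fat or other augmentation, and facial plastic surgery. The final list, including whether threads count, needs clinical input. It should be fixed before the interim database lock, since the interim analysis covers effectiveness (7.3.1).

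Score all other non-allowed treatments as observed. Replace the optional sensitivity analysis with a definite one that scores every observed Week 24 rating as it stands.

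The cost is a protocol amendment of a sentence or two and a flag derived from concomitant procedures already recorded in the eCRF (6.4.7). Response rates fall slightly, by at most the few subjects concerned. This changes scoring only and leaves the withdrawal rule untouched.

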#### Secondary effectiveness endpoints

All secondary effectiveness endpoints (see section 5.3.3) will be analyzed in an exploratory manner by means of descriptive statistics.

The descriptive tables will show the statistics described at the top of section 7.3 by time of assessments as well as for the changes from baseline (if applicable).

Concerning the follow-up for initial treatment, the last measurements / assessments before first treatment are defined as baseline. Concerning the time after repeat-treatment, the measurements / assessments at Visit RT1 before first repeat-treatment are defined as baseline.

Assessments on the MVDSS (see section 6.4.13) as well on the modified GAIS (see section 6.4.16) will be presented for each possible category. In addition, shift tables from baseline will be provided for the assessments on the MVDSS.

Concerning nasolabial folds measured by NLF-SRS based on the blinded evaluator's live assessment, shift tables from baseline will be presented for Week 4, 8, 16, 24, 36, and Week 48 after last injection of initial treatment phase.

Volume change measurements will be presented for each of the specified areas of interest (left side, right side, and total) at each time of assessment including change from baseline (see section 6.4.12).

The subject's satisfaction with overall treatment outcome will be evaluated based on the scores for 6 positively worded items that ask the subjects to indicate how they feel about the result of their most recent facial aesthetic procedure (FACE-QTM "Satisfaction with Outcome", see section 6.4.17).

Correspondingly, the subject's satisfaction with overall midface augmentation will be evaluated based on the scores for 5 items concerning the appearance of cheeks (FACE-QTM "Satisfaction with Cheeks", see section 6.4.18).

Concerning each injection, the subject's assessment of pain intensity on the Numeric Pain Rating Scale will be described at each time of assessment (immediately after the injection and after 15-minute intervals up to 60 minutes post-treatment) (see section 6.4.14).

The injection volume applied (right midface, left midface, and total), the duration of each injection as well as the injection technique and details concerning the injection equipment will be summarized for each injection time point and treatment group (see section 6.4.9).

In addition, at least the following main secondary effectiveness endpoints will be compared between the treatment groups by means of 95% confidence intervals for the differences in

- proportion of subjects with response on the MVDSS as assessed by the blinded evaluator at the site
- proportion of subjects with response on the MVDSS as assessed by the independent blinded photographic reviewer
- mean change in midface volume deficit measured on the 5-point MVDSS and based on the blinded evaluator's live assessment
- proportion of subjects with global aesthetic improvement (in modified GAIS) as assessed by the subject
- proportion of subjects with global aesthetic improvement (in modified GAIS) as assessed by the blinded evaluator

This will be done for each time of assessment during follow-up for initial treatment.

The resulting 95% confidence intervals for proportions will be presented in forest plots and the boundaries of the confidence intervals evaluated with respect to their clinical relevance in an exploratory manner.

The investigational device during repeat-treatment phase (saypha® VOLUME Lidocaine) will be evaluated descriptively using the following other endpoints:

- The percentage of responders on the 5-point MVDSS, based on the *blinded evaluator's live* assessment at Week 4, 12 and 24 after last injection of repeat-treatment phase compared to the score at Visit RT1
- Mean change in midface volume deficit measured on the 5-point MVDSS and based on the blinded evaluator's live assessment at Week 4, 12, and 24 after last injection of repeat-treatment phase compared to the score at Visit RT1
- Shift from baseline (Visit RT1) in NLF-SRS based on the blinded evaluator's live assessment at Week 4, 12 and 24 after last injection during repeat-treatment phase
- The extent of subject's satisfaction with overall treatment outcome at Week 4, 12 and 24 after last injection of repeat-treatment phase as assessed by the subject using the Face-QTM Questionnaire "Satisfaction with Outcome"

- The extent of subject's appearance appraisal at Week 4, 12 and 24 after last injection of repeattreatment phase as assessed by the FACE-QTM questionnaire "Satisfaction with Cheeks" compared to the score at Visit RT1
- Subject evaluation of pain after each treatment (repeat and touch-up-treatment) on an 11-point scale, where 0 is no pain and 10 is the worst pain imaginable
- Injection volume required to achieve optimal aesthetic result at each treatment (repeat and touchup treatment together)

